#### 1.6 Analysis sets

#### 1.6.1 Intention-to-treat (ITT) analysis set

The ITT includes all study attacks from all participants who underwent randomization and who reported at least one study attack. The ITT analysis set will not exclude attacks with protocol deviations or use of rescue medication before the two-hour time point. The ITT data set will be used for analysis of the primary and secondary effectiveness end points.

If any subjects in the ITT population have a missing headache score at the two-hour time point, multiple imputation may be used to impute their headache score for the analysis of primary and secondary endpoints, as described in section 1.9.

#### 1.6.2 As-treated analysis set

The as-treated analysis set includes all participants who received a study device, whether or not it was the actual randomized device. Subjects will be grouped by the device they actually used. This analysis set will be used for assessment of safety.

#### 1.6.3 Per-protocol analysis set

The per-protocol analysis set includes all study attacks with a reported headache score at the twohour time point, in which:

- The participant started using the study device within five minutes of the beginning of aura and before development of moderate or severe pain
- The participant did not use rescue drugs before the two-hour assessment point
- There were no changes in concomitant preventive treatment during the study that might potentially affect response.
- There were no other major protocol deviations

When comparing the ITT and Per Protocol analysis sets, the impact of protocol deviations and user errors can be investigated with the aim of identifying potential improvements to the investigational device and instructions for use. The ITT analysis set will also be used to analyse the impact of protocol deviations on the outcome parameters (e.g. use of rescue medication during the first two hours and starting the use of the device after the onset of headache).

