INVESTIGATIONAL DEVICE	The active device (Rehaler) is a single-use medical device for home use for the treatment of acute migraine attacks with aura in participants of ages 18+.
	The mechanism of the Rehaler device is partial rebreathing.
Intended Use	The intended use application of the Rehaler is early treatment of acute attacks of migraine with aura in patients of ages 18+ to stop or alleviate migraine with aura attacks. The user breathes through the mouthpiece from the beginning of the aura symptoms until they disappear.

EXPECTED STUDY DURATION	Randomized controlled Stage (Stage 1): Estimated 15 months from Study Initiation to end of Stage 1.		
	Open-label extension (Stage 2): 12 months.		
OBJECTIVES	Collect clinical data on Rehaler's effectiveness and safety for the early treatment of migraine with aura, in adults.		
PRIMARY EFFECTIVENESS ENDPOINT	Absence of Moderate or Severe pain at 2 hours (AMSP2)		
MOST IMPORTANT SECONDARY ENDPOINT	Pain Freedom at 2 hours (PF2)		
SAFETY PARAMETERS	 Incidence of device- or treatment-related adverse events. Incidence of device- or treatment-related serious adverse events (SAEs) and/or serious adverse device effects (SADE). 		
SAMPLE SIZE	Minimum 174, maximum 220 (randomized participants)		
STUDY POPULATION	Adult migraine with aura patients, ages 18-65		
KEY INCLUSION CRITERIA	 Participant has migraine with typical aura (ICHD3 classification 1.2.1) with the additional criterion that a moderate or severe headache historically follows the aura in more than 75% of cases of aura, beginning between 10 and 60 minutes after aura onset. 3 or more migraine-with-aura attacks over the last six months. 		
KEY EXCLUSION CRITERIA	 15 or more headache days per month History of chronic pulmonary disease or severe cardiovascular disease Anaemia 		
TREATMENT	Treatment with the study device starting as early as possible after onset of aura, and continuing until the aura symptoms have disappeared		

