10.2 Hypothesis

It is the primary hypothesis of the study that early treatment with the Rehaler device increases the likelihood of having no or only mild headache two hours after starting the treatment, compared with a sham device. "Early treatment" is here defined as treatment that is initiated during the aura phase, within ten minutes of aura symptoms onset, and before the start of moderate or severe migraine

headache. The primary endpoint is the absence of moderate or severe pain at 2 hours (AMSP2) after early treatment.

The primary effectiveness hypotheses are:

H₀: p_{Rehaler} = p_{sham} (null hypothesis)

 $H_a: p_{Rehaler} \neq p_{sham}$ (alternative hypothesis)

Where:

p_{Rehaler} = proportion of attacks in the Rehaler group with AMSP2

p_{sham} = proportion of attacks in the sham group with AMSP2

The primary effectiveness hypothesis will be tested using a two-sided adjusted χ^2 test for clustered binary data developed by Donner and Banting (Donner and Banting, 1988), with a 5% level of significance.

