13.4.1 Stage 1 At-Home Activities

Participants are instructed to have a study device and the ePRO app at hand at all times, and at the onset of aura symptoms follow the Attack Checklist (see section 13.4.1.1) to start the treatment and the logging of the attack in the ePRO app.

In the following cases, the participant should NOT treat the attack with the study device or record it in the study diary app:

- 1) If there are no aura symptoms (these are pre-specified in the Instructions for Use and ICF)
- 2) If there is moderate or severe headache at the time the aura symptoms start
- 3) If they are not able to start treatment within 10 minutes of beginning of the aura symptoms

The start of treatment is counted as time point 0.

Data are collected via the ePRO app at specified time points (0, 1, 2, 24 and 48 hours). If the app is not available (e.g. internet connection issues), the patient should report the data in paper forms provided during Site Visit 1.

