16.8.3 Per-protocol analysis set

The per-protocol analysis set includes all study attacks with a reported headache score at the twohour time point, in which:

- The participant started using the study device within five minutes of the beginning of aura and before development of moderate or severe pain
- The participant did not use rescue drugs before the two-hour assessment point
- There were no changes in concomitant preventive treatment during the study that might potentially affect response.

• There were no other major protocol deviations

When comparing the ITT and Per Protocol analysis sets, the impact of protocol deviations and user errors can be investigated with the aim of identifying potential improvements to the investigational device and instructions for use. The ITT analysis set will also be used to analyse the impact of protocol deviations on the outcome parameters (e.g. use of rescue medication during the first two hours and starting the use of the device after the onset of headache).

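### The per-protocol set drops attacks started more than five and up to ten minutes after aura onset, although the hypothesis and the participant instructions allow them

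*SAP*

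**What the plan says.** **Per-protocol set.** SAP 1.6.3 keeps study attacks with a reported two-hour headache score in which "The participant started using the study device within five minutes of the beginning of aura and before development of moderate or severe pain". Protocol 16.8.3 says the same: "The participant started using the study device within five minutes of the beginning of aura". Both lists then require no rescue drug before two hours and no relevant change in preventive treatment. They close with "There were no other major protocol deviations".

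**Hypothesis.** Protocol 10.2 defines early treatment as "treatment that is initiated during the aura phase, within ten minutes of aura symptoms onset", and before moderate or severe headache begins.

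**Participant instruction.** Protocol 13.4.1 lists cases in which "the participant should NOT treat the attack with the study device or record it in the study diary app". The timing case is: "If they are not able to start treatment within 10 minutes of beginning of the aura symptoms". The protocol synopsis describes treatment as "starting as early as possible after onset of aura", and the Attack Checklist (13.4.1.1) likewise asks for an immediate start. Neither sets a five-minute limit.

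**Use of the set.** SAP 1.6.3 and protocol 16.8.3 say that by comparing the ITT and per-protocol sets "the impact of protocol deviations and user errors can be investigated", with a view to improving the device and its instructions. The primary hypothesis is tested on the ITT set (SAP 1.7.1), as are all hypothesis tests in SAP 1.7.3. SAP 1.9 repeats the primary test on the per-protocol set only if the primary test fails, for the sponsor's information and not in support of the study objective.

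**The concern.** A per-protocol set should contain the attacks that were treated as the protocol asks. Here its time limit is half the limit that the protocol gives to participants and builds into its hypothesis, and no section explains the difference. Some attacks handled within the rules therefore leave the set.

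What is at stake is the meaning of one comparison. If ITT and per-protocol results differ, the plan would read the difference as the effect of deviations and user errors. Part of it could instead come from attacks with no deviation at all, merely started later within the permitted window. A sponsor revising the device or its instructions on that basis could draw the wrong lesson.

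**Working it through.** The plan states no figure on this point, so the check sets the passages side by side.

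**Step 1. Classify an attack by start delay alone** (before moderate or severe pain, no other departure):

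| Delay from aura onset | Early treatment under protocol 10.2 | May be treated and recorded under protocol 13.4.1 | Meets per-protocol timing (SAP 1.6.3, protocol 16.8.3) |
|---|---|---|---|
| Up to 5 min | Yes | Yes | Yes |
| More than 5, up to 10 min | Yes | Yes | **No** |
| More than 10 min | No | No | No |

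The middle row is the contradiction. It covers (10 − 5)/10 = half of the permitted time window. That is a share of minutes, not of attacks.

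**Step 2. List what separates the two sets.** Attacks in the ITT set but not in the per-protocol set are those with:
- a start after more than 5 and up to 10 minutes (within the instruction);
- a start after more than 10 minutes (outside it);
- moderate or severe pain before the start;
- rescue medication before two hours;
- a relevant change in preventive treatment;
- another major deviation;
- no reported two-hour score.

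The first group contains neither a deviation nor a user error by the protocol's own rules. The comparison pools it with groups that do.

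**Step 3. Check the rest of the criterion.** The requirement to start before moderate or severe pain agrees with protocol 10.2. Only the number of minutes disagrees.

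**Step 4. Can the affected attacks be identified?** Yes. Participants estimate their delay at time 0 (protocol 13.10.4).

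**Step 5. Size, for illustration only.** The distribution of start delay is not given, so the share lost is an assumption, shown from 0% to 50%, with loss at random. The other inputs are from SAP 1.5: 136 analysable participants, one third each with one, two and three attacks, ICC 0.486, two-sided threshold 0.048, AMSP2 26% against 61%, PF2 12% against 30%. Responses were simulated as beta-binomial and tested with the Donner and Banting adjusted χ² using an estimated ICC (6,000 runs).

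| Attacks lost (assumed) | AMSP2 power | PF2 power |
|---|---|---|
| 0% | 99.6% | 83% |
| 10% | 99.3% | 80% |
| 25% | 98.7% | 76% |
| 40% | 97.1% | 69% |
| 50% | 95.1% | 62% |

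With no loss, SAP Table 1 gives 99.1% for AMSP2, which agrees closely, and 85.5% for PF2 against 82.9% here. The SAP does not say how it generated correlated responses, so the 2.6-point difference shows no error and does not bear on this point. The PF2 column is background, because the SAP plans no per-protocol test of PF2.

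**The case against.** **The five minutes may be deliberate.** The positive instruction is to start at once, and ten minutes is only the outer limit. The five-minute wording is the same in both documents, which makes a slip less likely. This stands as a possible explanation, but neither document gives it. Protocol 10.2 makes ten minutes part of the hypothesis itself, so a stricter set answers a different question from adherence.

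**No passage calls a start at five to ten minutes a deviation.** This is correct. The classification is implied by the word *other* in the last criterion and by the stated purpose of the comparison.

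**The effect of delay is examined elsewhere.** Exploratory endpoints 14 and 15 (protocol 11.4.1) relate AMSP2 and PF2 to treatment delay, and the ITT set is also to be used to study deviations. This stands and lowers the stakes. It also shows that the per-protocol set is not needed to study early starting.

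**Stronger readings that the documents do not support.** A reader might infer that trial success depends on the five-minute set, because the pass/fail criterion (protocol 16.7) speaks of use per protocol. That phrase describes how the device is used and does not name the analysis set. Protocol 16.1 and SAP 1.7.1 place the primary test on ITT. A reader might also infer that the five-minute limit governs the interim analysis, because the synopsis trigger mentions per-protocol data from two attacks. Protocol 16.3 and SAP 1.4 require at least one study attack, and SAP 1.4 applies the ITT principle. That is a separate inconsistency to resolve in its own right.

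**Conclusion.** The point holds as an unexplained contradiction, both within the protocol and between the protocol and the SAP. As defined, the per-protocol set does not measure adherence, and the ITT versus per-protocol comparison does not isolate what the plan says it will.

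The consequence is modest. No primary or secondary test is affected, and the one planned per-protocol test is informational and conditional on a failed primary test. Under random loss, that set would keep about 95% power for AMSP2 even if half the attacks were dropped. That figure rests on the SAP's planning assumptions and on an assumed share. No count of affected attacks can be derived from the documents. The main harm is to interpretation, with some loss of precision.

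**What to change.** Before unblinding, reconcile SAP 1.6.3 and protocol 16.8.3 with protocol 10.2 and 13.4.1, so that the per-protocol start window is the same as the one in the hypothesis and the participant instructions. Which time is clinically right is for the sponsor and the investigators; this point takes no view on it. If five minutes is meant as a stricter early-start analysis, define it as a separately named exploratory subset and state the reason. Choosing the window after unblinding would make it data-dependent.

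In either case, report the number of attacks started more than five and up to ten minutes after onset, by arm.

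Cost: one criterion in two documents, submission of the SAP change to the Competent Authorities (SAP 1.7.3), and handling of the protocol change under protocol 20.2. No new data collection is needed, because delay is already recorded at time 0.

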#### 1.6.4 Exploratory analysis set

The exploratory analysis data set will include both study attacks and training attacks, in order to investigate the effect of training. The exploratory data set will in all other respects be identical to the ITT analysis set, e.g. it will not exclude attacks with protocol deviations or use of rescue medication before the two-hour time point.

#### 1.7 Outcomes and Analysis

#### 1.7.1 Primary hypothesis

In line with earlier studies on aura-phase treatment (Bates D. et al., 1994; Olesen J. et al., 2004), the trial's **primary end point** will be absence of moderate or severe pain at 2 hours (AMSP2), ), i.e. the percentage of study attacks in which the participant reported absence of headache of moderate/severe intensity at 2 hours post-treatment initiation. "Study attacks" are all attacks treated and reported during Stage 1, apart from the first attack which is a training attack and is not included in the analysis.

The intention-to-treat (ITT) analysis set will be used for the primary effectiveness hypothesis test. The primary effectiveness hypothesis is:

 $H_0: p_{Rehaler} = p_{sham}$ 

 $H_a: p_{\text{Rehaler}} \neq p_{\text{sham}}$ 

Where:

pRehaler = proportion of attacks in the Rehaler group with AMSP2

psham = proportion of attacks in the sham group with AMSP2

The primary effectiveness hypothesis will be tested using a two-sided adjusted  $\chi^2$  test for clustered binary data (Donner and Banting, 1988) at a 5% level of significance.

If Pearson's chi-squared test statistic is written as  $\chi^2 = \sum_{i=1}^{G} \chi_i^2$  with G = the number of treatment groups, then the adjusted  $\chi^2$  approximately follows a chi-squared distribution with G-1 degrees of freedom and is calculated as follows (Donner and Banting, 1988):

$$\chi_A^2 = \sum_{i=1}^G \frac{\chi_i^2}{\overline{C_i}}$$

Where:

- $\overline{C}_{l} = \sum_{j=1}^{n_{i}} \frac{m_{ij}C_{ij}}{\sum m_{ij}}$
- $C_{ij} = 1 + (m_{ij} 1)\rho$
- G is the number of treatment groups
- ni is the number of individuals in group i
- ρ is the correlation coefficient between any two responses in the same individual
- mij denotes the number of observations for individual j in group i

The corresponding 95% confidence interval for the difference in proportion of attacks with AMSP2 between the Rehaler and sham groups will also be calculated as follows (Donner and Klar, 1993):

95% Confidence Interval:  $(\hat{p}_{Rehaler} - \hat{p}_{sham}) \pm 1.96 * \widehat{SE}(\hat{p}_{Rehaler} - \hat{p}_{sham})$ 

Where:

- $\hat{p}_{Rehaler}$  = observed proportion of attacks in the Rehaler group with AMSP2
- $\hat{p}_{sham}$  = observed proportion of attacks in the sham group with AMSP2

• 
$$\widehat{SE}(\hat{p}_{Rehaler} - \hat{p}_{sham}) = \left(\frac{\overline{C_1}\hat{p}_{Rehaler}(1 - \hat{p}_{Rehaler})}{n_1} + \frac{\overline{C_2}\hat{p}_{sham}(1 - \hat{p}_{sham})}{n_2}\right)^{1/2}$$

• 
$$\overline{C}_{l} = \sum_{j=1}^{n_{i}} \frac{m_{ij}C_{ij}}{\sum m_{ij}}$$

• 
$$C_{ij} = 1 + (m_{ij} - 1)\rho$$

- ni is the number of individuals in group i
- ρ is the correlation coefficient between any two responses in the same individual
- mij denotes the number of observations for individual j in group i

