16.2 Sample Size and Statistical Power

The study's key secondary endpoint is Pain Freedom at 2 hours (PF2). Recognizing that this is the ideal outcome for migraine patients, the study has been designed with a moderately high statistical power (80%) for PF2. The estimated study size of 174 included participants has been determined on the basis of data from the pilot study and post-market data collected in Denmark, Sweden and Germany from 2018 to 2020, indicating that the PF2 rate will be 30% in the active device group and 12% in the sham group, that each patient will contribute data from two attacks while in Stage 1, and that the total percentage of included patients not yielding analyzable data will be 30%. These data were utilized in a sample size analysis, conducted by simulation and using the χ^2 significance test adjusted for clustered data. Under the given assumptions and including 174 patients, the estimated power for PF2 is 80%. Pilot study and post-market data indicated an AMSP2 rate of 61% in the study will result in 95% power for AMSP2. Therefore, the clinical investigation will randomize at minimum 174 participants.

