### 1.5 Power and sample size calculation

#### 1.5.1 Assumptions

The estimated study size of 200 to 240 included participants has been determined on the basis of data from the pilot study (Fuglsang et al., 2018) and post-market data collected in Denmark, Sweden and Germany from 2018 to 2020.

To estimate the sample size for this trial, it was assumed that 12% of subjects in the sham group and 30% of subjects in the active group would experience PF2. For AMSP2, a 26% response rate in the sham group and a 61% response rate in the active group was assumed.

The primary statistical test for this analysis will be a  $\chi^2$  significance test adjusted for clustered data (using the methods of Donner and Banting (Donner and Banting, 1988)) since subjects could contribute more than one migraine attack. The intraclass correlation coefficient (ICC) from preliminary data on this device was 0.486. This is a group-sequential design with one interim analysis, so the O'Brien Fleming Spending function will be used to set significant thresholds of 0.0052 at the interim analysis and 0.048 at the final analysis.

Power and sample sizes were estimated via simulation using the above parameters for a  $\chi^2$  significance test adjusted for clustered data. These simulations assumed a third of subjects would have one migraine attack during the course of the study, a third of subjects would have two study attacks, and a third of subjects would have three study attacks. In the interim analysis, a more refined method of estimating number of attacks per participant will be employed, using the observed attack frequencies from the interim data (cf. section 1.4). Additionally, it was expected that 22% of subjects would drop out of the trial and 10% of attacks would have missing data at the 2 hour time point, for a total of 32% of randomized subjects that would not provide data usable for the statistical analysis of the primary or secondary endpoint.

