| Categorical      | 
 
Headache Score at 2 hours (HS2)
 
Most Bothersome Symptom Score at 2 hours (MBS2)
 
Functional Disability Score at 2 hours (FDS2)
 
Participant Satisfaction at 48 hours (PS48)
 
Light Sensitivity Score at 2 hours (LSS2)
 
Nausea Score at 2 hours (NS2)
 
Sound Sensitivity Score at 2 hours (SSS2)
 
 | Ordinal logistic regression using the
proportional odds model with device type
(active or sham) as the exposure variable.
Threshold p value: 0.05   |

Table 3: Hypothesis testing for primary and secondary endpoints

The following Stage 2 exploratory endpoints will be compared to corresponding baseline values reported at Site Visit 1:

- How many times in the past month has the participant taken respectively a prescription acute migraine drug or an over-the-counter acute analgesic, with the intention to treat migraine.
- Proportion of patients who used an opioid drug to treat migraine the past month
- Proportion of patients who have been hospitalized for migraine in the past month

All hypothesis tests will be performed on the ITT data set of attacks. In the resulting data set each attack will constitute a data point and each patient will constitute a cluster including from one to three data points. The statistical analysis will take clustering into account by using the adjusted  $\chi^2$  statistic for clustered binary data developed by Donner and Banting (Donner and Banting, 1988) and validated by others (Gonen et al., 2001; Jung et al., 2001). This method negates the risk of type I errors that is incurred if clustering is disregarded. In the event that changes are made to the statistical analysis plan, these changes will be submitted for approval to the Competent Authorities.

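### The 95% CI for the AMSP2 difference divides an attack-level variance by the number of participants, making it about 1.4 times too wide and inconsistent with the primary test

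*SAP*

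**What the plan says.** SAP 1.7.1 tests AMSP2 with an adjusted chi-square for clustered binary data and then defines "The corresponding 95% confidence interval for the difference in proportion of attacks with AMSP2" between the groups as the observed difference ± 1.96 × SE. The SE is the square root of the sum over the two arms of `C_i` × p(1−p) / `n_i`.

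The symbols are defined in words:

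- p is the "observed proportion of attacks in the Rehaler group with AMSP2", and likewise for sham.
- `C_i` is the attack-weighted mean of 1 + (`m_ij` − 1)ρ, where `m_ij` "denotes the number of observations for individual j in group i".
- `n_i` "is the number of individuals in group i".

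Protocol 16.1 gives the same SE formula and the same definition of `n_i`. SAP 1.7.3 fixes the unit of analysis: "each attack will constitute a data point and each patient will constitute a cluster including from one to three data points".

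**The concern.** The p and `C_i` in this formula are attack-level quantities, but the divisor counts participants. The formula therefore charges the penalty for correlated repeat attacks (through `C_i`) without crediting the extra observations. The interval would widen as participants contribute more attacks, when it should narrow.

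The SAP presents this interval as the counterpart of the primary test, but the test is computed on attacks, so the two rest on different variances. At stake are the reported precision of the primary effect and the risk of a report in which the primary test is significant while its own CI includes zero.

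**Working it through.** **Inputs.** From SAP 1.5.1: AMSP2 61% active and 26% sham; ICC 0.486; one, two or three attacks, a third of participants each (mean 2); final threshold 0.048. From SAP Table 1: 136 evaluable at 200 randomized, so 68 participants and 68 × 2 = 136 attacks per arm. Protocol 16.2 also plans for two attacks per participant.

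**1. The correct variance.** For a proportion of attacks with within-participant correlation ρ:

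Var(p_i) = p(1−p) × Σ`m_ij`[1 + (`m_ij` − 1)ρ] / (Σ`m_ij`)² = `C_i` × p(1−p) / Σ`m_ij`.

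The divisor is total attacks. With the same mean attacks in both arms, the written SE is too large by √(mean attacks): 1.00 at a mean of 1, 1.22 at 1.5, 1.41 at 2 and 1.73 at 3.

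**2. Which denominator the planning used.** The documents state no CI width, so the nearest stated figure is AMSP2 power of 99.1% at 200 randomized. With C = 1.648 (step 3), attack denominators give an effective 136/1.648 = 82.5 per arm and power of 99.7% (99.6% simulated). Participant denominators give 68/1.648 = 41.3 and 90.6%. Not every cell of Table 1 reproduces: PF2 at 200 is stated as 85.5% against 81.1% computed, and AMSP2 at 100 as 85.2% against 90.5%. Participant denominators reproduced none of the cells checked.

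**3. Size at the planning values.**

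- C = (1×1 + 2×1.486 + 3×1.972)/6 = 1.648
- v = 0.61×0.39 + 0.26×0.74 = 0.4303
- SE as written = √(1.648×0.4303/68) = 0.1021; half-width 20.0 points; CI 15.0 to 55.0
- SE corrected = √(1.648×0.4303/136) = 0.0722; half-width 14.2 points; CI 20.8 to 49.2

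At 240 randomized (0.68 × 240/2, about 82 per arm), the half-widths are 18.2 and 12.9 points.

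**4. Response to more data.** 68 participants per arm, the same number of attacks from each:

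| Attacks each | C | Half-width as written | Corrected |
|---|---|---|---|
| 1 | 1.000 | 15.6 | 15.6 |
| 2 | 1.486 | 19.0 | 13.4 |
| 3 | 1.972 | 21.9 | 12.6 |

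With ρ = 0 and two attacks each, the figures are 15.6 and 11.0, so correlation is not the source of the gap.

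**5. Coverage.** Simulated trials at the planning values used beta-binomial responses and an ANOVA estimate of ρ; both are assumptions not in the documents. In a 20,000-trial run the true SD of the difference was 0.0720, the mean corrected SE 0.0717 and the mean written SE 0.1013. Across repeat runs, coverage was 99.1 to 99.3% as written and 94.3 to 94.6% corrected.

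**6. Agreement with the test.** With sham at 26%, the test is significant from a difference of 14.5 points. The written CI excludes zero only from 20.3 points; the corrected CI does so from 14.2. Simulated over 10,000 trials per row, 68 per arm, with the last column at 0.048:

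| Active vs sham | Test significant | Significant, but written CI includes zero | Same, corrected CI |
|---|---|---|---|
| 61% vs 26% (planned) | 99.5% | 2.3% | 0% |
| 55% vs 26% | 97.0% | 9.9% | 0% |
| 50% vs 26% | 89.5% | 20.6% | 0% |
| 45% vs 26% | 72.1% | 28.3% | 0% |

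The last three rows are scenarios chosen for this check; the documents do not give those rates. At the planned effect the disagreement is 0.1% at ρ = 0.01, 0.3% at ρ = 0.2 and 4.5% at ρ = 0.7.

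**The case against.** The strongest reply is that little depends on this interval. The error is conservative. The step-down in SAP 1.7.3 runs on hypothesis tests, the pass/fail criterion in Protocol 16.7 compares percentages, and SAP Table 3 also calls for odds ratios. A programmer working with one row per attack might notice the slip. All of this limits the severity, but both documents prescribe this exact calculation, and neither gives a correct denominator elsewhere. A misread symbol is not the explanation either: `n_i` is defined in words and is also the upper limit of the sum over participants.

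Four narrower points stand:

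- The factor √(mean attacks) is exact only when the arms have equal means; otherwise it lies between the two arms' square roots. If the 10% missing two-hour scores in SAP 1.5.1 are applied per attack, it is 1.37.
- At the planned effect, test and CI seldom disagree. The larger rates depend on smaller effects that the plan does not assume.
- Correcting the denominator does not make CI and test identical. The CI uses 1.96 while the threshold of 0.048 implies 1.977, and its variance is unpooled while the test's is pooled. The corrected CI excluded zero beside a non-significant test in 0.01% of simulated trials at 61% vs 26% and in 1.45% at 45% vs 26%.
- No stated number is wrong. This is an error in a formula's definition.

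**Conclusion.** The concern holds. The interval specified for the primary endpoint uses the wrong denominator in both documents. At the planned mean of two attacks its half-width is about 1.4 times what it should be (20.0 against 14.2 points at 200 randomized), with coverage near 99%. That result is algebraic and needs only equal mean attacks per arm; the coverage and disagreement rates also rest on the simulation assumptions above. The primary test, its type I error, the stated power and the labelling sequence are unaffected. It should be corrected because it misstates the precision of the main result and can appear to contradict a significant test.

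**What to change.** In the SE formula in SAP 1.7.1 and Protocol 16.1, replace `n_1` and `n_2` with the total number of study attacks analysed in each group, `M_i` = Σ`m_ij`, and define that symbol. Keep `n_i` only as the summation limit in `C_i`.

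The cost is one line in each document, with no extra patients or data. SAP 1.7.3 sends SAP changes to the competent authorities for approval, so this would follow that route. It should be done before the final unblinded analysis, since narrowing a primary-endpoint CI afterwards would look post hoc.
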